FULL TITLE OF THE STUDY

How has the increased use of FFP3 style respirators during the COVID-19 Pandemic affected hospital doctor's facial hair? Implications for staff safety and welfare.

SHORT STUDY TITLE / ACRONYM

Facial Hair, PPE and COVID-19

RESEARCH REFERENCE NUMBERS

IRAS Number: 283609

SPONSORS Number: TBC

FUNDERS Number: N/A

This protocol has regard for the HRA guidance and order of content

LIST of CONTENTS

GENERAL INFORMATION	Page No.
HRA PROTOCOL COMPLIANCE DECLARATION	1
TITLE PAGE	1
RESEARCH REFERENCE NUMBERS	1
LIST OF CONTENTS	2
KEY STUDY CONTACTS	3
STUDY SUMMARY	3
SECTION	
1. BACKGROUND	4
2. RATIONALE	4
3. RESEARCH QUESTION/AIM(S)	4
4. STUDY DESIGN/METHODS	4
5. SAMPLE AND RECRUITMENT	5
6. ETHICAL AND REGULATORY COMPLIANCE	6
7. DATA PROTECTION AND PATIENT CONFIDENTIALITY	7
8. DISSEMINATION POLICY	7
9. REFERENCES	7
10. APPENDICES	8

KEY STUDY CONTACTS

Chief Investigator	[name] Royal Cornwall Hospital
Study Co-ordinator	As above
Sponsor	[name] Research Development and Innovation Department [name] Royal Cornwall Hospital Trust [name] [contact] [name]
Funder(s)	N/A
Key Protocol Contributors	[name] – Trust bank doctor , [contact] [name] – Trust bank doctor , [contact] [name] – Trust bank doctor , [contact] [name] – Foundation year doctor , [contact]

STUDY SUMMARY

Study Title	How has the increased use of FFP3 style respirators during the COVID-19 Pandemic affected hospital doctor's facial hair? Implications for staff safety and welfare.
Internal ref. no. (or short title)	Facial Hair, PPE and COVID-19
Study Design	A single site, cross-sectional questionnaire
Study Participants	Trust staff with facial hair required to use PPE due to COVID-19
Planned Size of Sample (if applicable)	N/A
Follow up duration (if applicable)	N/A
Planned Study Period	1 Month
Research Question/Aim(s)	To assess how the increased use of FFP3 style respirators during the COVID-19 Pandemic has affected hospital doctor's facial hair?

STUDY PROTOCOL

How has the increased use of FFP3 style respirators during the COVID-19 Pandemic affected hospital doctor's facial hair? Implications for staff safety and welfare.

1 BACKGROUND

The importance of effective personal protective equipment (PPE) has been highlighted during the COVID-19 global pandemic. Part of this equipment has been the use of filtering facepieces class 3 (FFP3) masks, which are particularly important to those staff undertaking "aerosol generating procedures" (AGP) such as chest compressions, intubation or endoscopy.¹ However, for effective use, these need to be "fit tested" to the individual, which involves using a test aerosol to assess the efficacy of the mask. It is widely accepted that facial hair affects the effectiveness of these masks,^{2,3} and there is clear guidance from Public Health England regarding which facial hair styles are likely to pass and fail fit testing.¹ However, there is little data reporting the adherence of this guidance, especially for hospital doctors for whom this guidance is relevant.

The research question is to assess whether these guidelines are being followed during this global pandemic, and if not, explore the reasons this may be the case. This has implications as FFP3 masks are not the only form of PPE for the face, and this study may highlight a need for employers to diversify which PPE they supply to their employees, such as full hoods.⁴

We will be targeting hospital doctors, as they are front line staff whom the FFP3 guidance directly affects. There may be implications from this research regarding the forms of PPE that are being supplied to employees, especially if there are particular reasons that employees have for maintaining their facial hair. The implications also include provision of alternative PPE for those who have failed fit testing.

2 RATIONALE

COVID-19 is a highly contagious virus which has caused a global pandemic. There have been significant health consequences for healthcare workers, which may be related to the provision of personal protective equipment (PPE). Following PPE guidance is a significant health and safety concern, under which facial hair guidance for tight fitting masks falls.

This has implications as FFP3 masks are not the only form of PPE for the face, and this study may highlight a need for employers to diversify which PPE they supply to their employees, such as full hoods if staff need to maintain facial hair for cultural or religious reasons.

3 RESEARCH QUESTION/AIM(S)

How has the increased use of FFP3 style respirators during the COVID-19 Pandemic affected hospital doctor's facial hair?

Is there a difference between the prevalence of altered facial hair among those expected to perform aerosol generating procedures when compared to those who are not?

Are there doctors at RCHT who report religious or cultural reasons to changing their facial hair?

Have alternative forms of PPE been offered to those who do not achieve an adequate fit with FFP3 respirators?

3.1 Objectives

To understand if the current PPE FFP3 guidance is suitable for everyone it is intended for. Anyone with facial hair and in particular, the effects on those whose ethnic or religious beliefs prevent them from removing any facial hair.

3.2 Outcome

To see if having facial hair in any context affected appropriate use of the FFP3. Consideration will also be given to if the current guidance is broad enough to offer an equal and diverse option of PPE FFP3 to all, in particular those with specific cultural, personal and ethnic needs and if not, what options can be taken to ensure that all staff needs are supported. Secondly, we will be looking to measure the personal impact on individuals having to remove facial hair because of the guidance and advice currently offering only one source of protection.

4 STUDY DESIGN and METHODS of DATA COLLECTION AND DATA ANALYSIS

The study design will be a cross sectional study in the form of a single survey.

The population of interest are all hospital doctors at a Royal Cornwall hospital. A list of these doctors will be provided by the postgraduate centre, and an email, detailing the purpose of the research and an information sheet, will be circulated to these doctors, informing them that their participation is voluntary. In this email, there will be a link to a questionnaire which will take approximately 5 minutes to complete. The participants will not be required to input any identifiable information, so data will be anonymous to the researchers. Participants will be asked demographic questions such as age, gender, grade, department and whether they have the potential to be involved in aerosol generating procedures (AGP). They will also be asked if they passed fit testing, the most common level of PPE they wear at work, and whether they have been offered an alternative to a FFP3 mask. The participants will then be asked if they are able to grow facial hair, and if so they will be asked to select from a chart (taken with permission from Public Health England guidance) the styles which most resembled their facial hair before and after the first cases of COVID-19 were treated in our hospital. Participants will then be asked if their facial hair was influenced by FFP3 guidance, if they are happy with their current style, if they have any religious or culture reasons for maintaining their style, and whether there have been any religious, emotional or wellbeing effects to changing facial hair style. They will then be asked to select from a separate chart their favourite facial hair style, followed by any optional free text responses. The study will only be asking about FFP3 style respirator face protector PPE, and not any other form of protective equipment which may affect patient's hair.

We have deliberately included all genders as not everybody identifies as either male or female, and the ability to grow facial hair is not limited to men. We have considered that we may offend female members of staff, however the email is generic to all doctors and not targeted to specific people. We also ask the question as such, "Do you grow facial hair which you can stylise? (This includes facial hair that you regularly shave, but does not include vellus or downy hair)". Our aim is to be as inclusive as possible, but to also not offend an already marginalised group of society (i.e. those who do not identify as either male or female). We suspect most of our responses will be from those identifying as male, but did not want to limit our population responses to this.

Data will be imported into Microsoft Excel, and statistical analysis will be performed using the R and R studio software packages. The odds ratio and relative risk will be calculated of a self-reported change in facial hair style in those who wore an FFP3 appropriate facial hair style prior to the COVID-19 pandemic versus those who did not, among the responders to the survey who reported they were able

to grow facial hair. Researchers will also calculate the odds ratio of a reported facial hair change in those expected to perform aerosol generating procedures versus those who were not. Confidence intervals will be calculated at the 95% confidence level. All statistical analysis will be performed by the researchers.

Once the study has ended and the final analysis of the project has concluded, the study documents will be archived for a minimum of 5 years in line with the Trust archiving Standard Operating Procedure RD&I SOP-07.

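### The AGP item has no reference date while the facial-hair outcome has one, so the exposure for the second research question is recorded after fit testing and the hair decision, and its odds ratio may be biased in either direction

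*Protocol*

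**What the plan says.** All points are in Section 4 of the protocol unless stated.

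- Data are collected once: "The study design will be a cross sectional study in the form of a single survey".
- The outcome is tied to a local event. Respondents pick from a chart the styles closest to their own "before and after the first cases of COVID-19 were treated in our hospital".
- The AGP item is listed with age, gender, grade and department, and asks "whether they have the potential to be involved in aerosol generating procedures (AGP". No reference date is given.
- Fit testing is asked about as a past event: "They will also be asked if they passed fit testing, the most common level of PPE they wear at work". A further item asks "whether they have been offered an alternative to a FFP3 mask".
- The analysis of the second research question (Section 3) is "the odds ratio of a reported facial hair change in those expected to perform aerosol generating procedures versus those who were not". No other estimator is given for that question, and this wording does not fix a time for AGP status either.
- Section 1 gives the background: FFP3 masks matter particularly for AGP work and have to be fit tested, and "It is widely accepted that facial hair affects the effectiveness of these masks".

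No item on AGP status at the start of the pandemic, or on a later change of duties, is described. The questionnaire is listed in Section 11.1 but is not shown.

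**The concern.** An exposure should be fixed before the outcome it is compared against. Here the hair change may have happened at any time since the first local cases, while AGP status is taken, on the protocol's description, as it stands when the form is filled in. The protocol's own background links the two. AGP work relies on a fit-tested mask, facial hair impairs that mask, and Section 3.1 singles out doctors whose beliefs prevent them from removing facial hair. A doctor who kept an unsuitable style might have come off AGP work, and one who shaved and passed might have come onto it. AGP status would then be partly a consequence of the hair decision.

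The comparison of AGP with non-AGP doctors is the whole answer to the second research question. If some of the difference came from movement after the hair decision, the planned odds ratio could not show it. Later analysis could not put it right either. The baseline status would not be in the data, and the responses are anonymous (Sections 4 and 5.3.1), so respondents could not be identified and asked again.

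**Working it through.** **The protocol's own figure.** Section 5.2.1 expects 20% of 1025 doctors: 1025 × 0.20 = 205, as stated. The protocol gives no AGP share, change rate, rate of changed duties or target odds ratio, so every input below is an assumption.

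**Timing.** Outcome: two dated points, before and after the first local cases. Fit test: past tense. AGP status: present tense, undated. Read together, AGP status is the last of the three to be fixed.

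**Set-up (assumed).** 100 doctors able to grow facial hair, 60 in AGP roles at the first cases and 40 not, with 40% changing style in both groups.

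| | Changed | Not changed |
|---|---|---|
| AGP | 24 | 36 |
| Non-AGP | 16 | 24 |

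True odds ratio = (24 × 24)/(36 × 16) = 1.00.

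Let m be the net number of non-changers who move from the AGP row to the non-AGP row before the survey. Then

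observed OR = 24 × (24 + m) / [16 × (36 − m)].

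**Who could move for a hair-related reason.** Non-changers include doctors whose style already suited the mask. They had no facial-hair reason to leave AGP work. Suppose 24 of the 36 were in that position, leaving 12 who kept an unsuitable style.

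| Share of the 12 leaving | m | Calculation | Observed OR |
|---|---|---|---|
| 10% | 1.2 | (24 × 25.2)/(16 × 34.8) | 1.09 |
| 20% | 2.4 | (24 × 26.4)/(16 × 33.6) | 1.18 |
| 30% | 3.6 | (24 × 27.6)/(16 × 32.4) | 1.28 |

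**If all 36 non-changers could move.** 10%, 20% or 30% leaving means m = 3.6, 7.2 or 10.8, and the odds ratio is 1.28, 1.63 or 2.07. The last case needs 10.8 of the 12 hair-keepers, or 90%, to leave if only hair-keepers move. These values are upper illustrations.

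**Other movements.**
- Each leaver replaced by an already compliant doctor who also did not change: m = 0, odds ratio 1.00.
- Net inflow of 3.6 non-changers into AGP work (m = −3.6): (24 × 20.4)/(16 × 39.6) = 0.77.
- With 205 analysable doctors, half AGP and 30% changing in each group, a net move of non-changers equal to 10% of the AGP group gives 1.33 if outward and 0.75 if inward.

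**Against sampling error.** Woolf standard error of the log odds ratio in the 60/40 table: √(1/24 + 1/36 + 1/16 + 1/24) = 0.417. The 95% interval around 1.00 is exp(±1.96 × 0.417), or 0.44 to 2.26. For the 205-doctor table it is 0.55 to 1.82. Shifts of 1.09 to 1.28 lie inside both.

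**The case against.** The strongest reply is that a reader might infer that doctors who kept their hair were taken off AGP work, so that the odds ratio is inflated. The protocol does not support that.

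- No section says that duties changed after a failed fit test. That objection stands: movement is an assumption.
- The item asks about potential involvement and sits among the demographic questions, so it may be read as an attribute of the role. Section 1 counts chest compressions as an AGP, so a doctor moved off planned AGP work could still answer yes. A doctor given an alternative to FFP3 could also stay on AGP work. Both points stand and make any shift smaller, but neither dates the item.
- Direction is not settled, as the working shows. This stands against a claim of inflation. It does not remove the problem, because the investigators could not tell bias from a true difference.
- The shift is within sampling error at these sample sizes. That is true on the assumed inputs, but a confidence interval makes no allowance for bias.
- The research question asks about a difference in prevalence, and weak time ordering comes with a single survey. This stands in part. The result should be presented as an association, but the order can still be improved by dating one item.
- The survey-day reading rests on the protocol's summary of the item. If the questionnaire already carries a date, only Section 4 needs correcting.
- An anchor at the first cases alone would count doctors who took on AGP work later as unexposed, and would leave later joiners, who are eligible under Section 5.1.1, with no valid answer. This stands and shapes the fix.

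**Conclusion.** The point holds as a possible bias of unsettled direction. As described, the AGP exposure is undated and recorded after fit testing and the hair decision, while the outcome is dated. Whether this distorts the odds ratio depends on whether those events altered AGP status, which the protocol does not say. If hair-keepers left AGP work on net, the odds ratio rises. If leavers were replaced one for one by compliant non-changers, it does not move. If non-changers moved into AGP work on net, it falls.

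On the assumed 60/40 split with 12 hair-keepers, a true odds ratio of 1.00 would be seen as about 1.09 to 1.28 when 10% to 30% of them leave. The values up to 2.07 require movement among doctors with no facial-hair reason to move, or nearly all hair-keepers leaving, and should not be quoted as the expected size. The change is worth making because it is cheap before launch and cannot be made afterwards.

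**What to change.** In Section 4 and in the questionnaire:

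1. Date the exposure item, for example: *At the time this hospital treated its first COVID-19 patients (or when you joined, if later), were you expected to carry out AGPs, leaving aside any fit-test result and any later change of duties?* This also brings the item into line with the analysis wording, which speaks of expectation rather than potential.
2. Add one item on AGP status now, or on any change since that time.
3. Use the first item as the exposure in the planned odds ratio, and report the same odds ratio under the second as a sensitivity analysis.
4. Describe the result as an association.

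**Cost.** One reworded item, one extra item in a questionnaire of about 5 minutes, and a sentence or two in Section 4. There will be some recall error. Doctors who took on AGP work later, including any who shaved for it, count as unexposed in the main analysis; the sensitivity analysis shows how much that matters. For late joiners, status at joining may still follow a hair change made elsewhere, so some uncertainty about order remains.

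### The stated aim of exploring why the guidance is not followed is broader than the one reason item described, which covers religious or cultural reasons only

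*Protocol*

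**What the plan says.** Section 1 (Background) states the purpose in two halves. The first is adherence to the guidance; the second is the explanation for non-adherence: "and if not, explore the reasons this may be the case". It links the practical value of the study to what those explanations turn out to be, "especially if there are particular reasons that employees have for maintaining their facial hair", and does not confine them to religion or culture.

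Section 3 (Research question/aims) is narrower: "Are there doctors at RCHT who report religious or cultural reasons to changing their facial hair". Section 3.1 (Objectives) looks at "in particular, the effects on those whose ethnic or religious beliefs prevent them from removing any facial hair". Section 3.2 (Outcome) asks whether the guidance offers suitable options to all staff, "in particular those with specific cultural, personal and ethnic needs".

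Section 4 (Study design and methods) describes the questionnaire in prose. One item asks for a reason to keep a style: "if they have any religious or culture reasons for maintaining their style". The items around it cover influence of the guidance and satisfaction ("Participants will then be asked if their facial hair was influenced by FFP3 guidance, if they are happy with their current style"), effects of having changed style, and favourite style. Earlier items cover AGP potential, fit-test result, usual PPE level and whether an alternative to an FFP3 was offered. The questionnaire ends with an optional free-text field. The full questionnaire is listed as an appendix document and is not reproduced.

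**The concern.** A reason that is not asked about cannot be counted. If only religious and cultural reasons have their own item, they are the only ones whose frequency the study can report, although sections 1 and 3.2 promise something wider. This matters because sections 1 and 2 intend the results to inform employers whether to diversify the PPE they supply. A doctor who keeps a beard for identity, because of a skin condition, or because the guidance never reached them may need a different response from one who keeps it for religious reasons.

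This cannot be left to the analysis stage. The survey is single and anonymous, so respondents cannot be contacted again and no later analysis can recover a reason that was not collected.

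**Working it through.** The point concerns questionnaire content, so the check sets the aims beside the items described.

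**The only relevant figure.** Section 5.2.1 expects 1025 × 0.20 = 205 respondents, which reproduces the stated figure. The protocol does not say how many of these would currently wear a style that is not FFP3-appropriate, nor how reasons would be distributed among them. The size of the gap therefore cannot be calculated.

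**Aims against items.**

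| Possible reason or circumstance | Named in the aims | Item described in section 4 | Recorded as a reason? |
|---|---|---|---|
| Religious | Sections 2, 3, 3.1 | Yes | Yes |
| Cultural | Sections 2, 3, 3.2 | Yes | Yes |
| Ethnic | Sections 3.1, 3.2 | None separate; may overlap with cultural | No, unless reported as cultural |
| Personal or identity | Section 3.2 (personal) | Satisfaction and favourite style only | No |
| Skin or medical | Only within the general aim of section 1 | None | No |
| Not aware of the guidance | Only within the general aim of section 1 | Influence of guidance only | No |
| FFP3 not needed, or other PPE used | Section 3 asks whether alternatives were offered | AGP potential, usual PPE level, alternative offered | Circumstance only |
| Passed fit test | Not named as a reason | Fit-test result, not described as tied to a style | Circumstance only |

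**What the neighbouring items add.** Influence of guidance, satisfaction and favourite style measure attitude or preference. The item on religious, emotional or wellbeing effects records consequences of changing, not why someone kept a style. The fit-test, PPE-level, AGP and alternative items allow a useful cross-tabulation with current style, but they do not show that the circumstance was the doctor's reason.

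**What free text can deliver.** Let n be the respondents with a non-appropriate current style, k those who mention reason R in free text, and m those who leave the field blank. A blank is not a denial, so the proportion holding R is at least k/n and could be as high as (k + m)/n, or higher if some who wrote about something else also hold R. The range is at least m/n wide whatever the sample size, and a confidence interval around k/n would not reflect it. A tick list shown to all n removes most of this uncertainty, because an unticked box on an answered list can be read as a no.

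**The case against.** The strongest reply is that section 3, the formal statement of the questions, limits reasons to religious or cultural ones, and the rationale in section 2 uses the same pair. On scope, the item does what section 3 needs. The broader wording sits in the background and in an outcome section that promises only to give consideration to the breadth of the guidance. This stands in part: the item is not wrong for section 3. But section 1 calls the wider purpose the research question, and section 3.2 adds personal and ethnic needs, so the protocol is inconsistent and its data collection follows the narrow version. The match with section 3 is also one of scope only, since section 3 speaks of changing facial hair and the item of maintaining it.

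Second, section 4 asks about fit testing, PPE level, AGP potential and alternatives. This stands. A reader might infer that non-adherence could be reported only as religious, cultural or unexplained, or that a doctor who does not use an FFP3 would appear to be disregarding the guidance. The document does not support either inference, because those items identify such circumstances.

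Third, the questionnaire is not shown, and a prose summary does not exclude an 'other' option. This also stands, and it limits the point to what the protocol describes.

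**Conclusion.** The point holds as a mismatch between aim and measurement. As described, the survey can count religious or cultural reasons. It can cross-tabulate fit-test and PPE circumstances with style. It cannot estimate how often personal or identity, ethnic, or skin or medical reasons, or unawareness of the guidance, lie behind a non-appropriate style.

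A reader might go further and conclude that most reasons will go unrecorded. The protocol does not support that: it gives no distribution of reasons and no count of doctors with a non-appropriate style, free text can catch some of the remainder, and 'cultural' may absorb part of 'ethnic'. The share affected is unknown.

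The conclusion assumes that the questionnaire follows the prose in section 4 and has no further reason options. The change is worth making before launch because a stated aim would otherwise not be properly measured. The planned comparisons of facial hair change, by prior style and by AGP expectation, do not use this item and are unaffected.

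**What to change.** Before launch, for respondents whose current style is not FFP3-appropriate, replace the item with a tick-all-that-apply list: religious; cultural; ethnic; personal or identity; skin or medical; not aware of the guidance; FFP3 not needed or other PPE used; other (specify). The chart answer for style after the first cases can define this group, using the same appropriate/not-appropriate classification that section 4 already applies to the earlier style. Other respondents keep the present item, so the religious or cultural question in section 3 can still be answered for everyone who grows facial hair.

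Report each reason as a proportion of the respondents with a non-appropriate style, with a 95% confidence interval, and cross-tabulate it with the existing fit-test and PPE items. Categories can overlap, so the proportions need not add to 100%.

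If the questionnaire cannot be changed, narrow the aims in sections 1 and 3.2 to religious or cultural reasons, as in section 3, and present anything from free text as descriptive comment without a frequency.

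The cost is one reformatted item and a few seconds of response time in a survey expected to take about 5 minutes. Section 4 already shows the style questions only to those who can grow facial hair, so a conditional item is in keeping with the design.

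### The only described item on religious, emotional or wellbeing effects depends on having changed style, so doctors who kept facial hair for religious or cultural reasons have no structured item for such an effect

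*Protocol*

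**What the plan says.** Section 3.1 of the protocol asks whether the FFP3 guidance suits everyone it is meant for. It gives particular weight to "the effects on those whose ethnic or religious beliefs prevent them from removing any facial hair". Section 3.2 adds a second outcome, to "measure the personal impact on individuals having to remove facial hair because of the guidance".

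Section 4 describes the questionnaire in running prose. On respirators: "They will also be asked if they passed fit testing, the most common level of PPE they wear at work", plus whether an alternative to an FFP3 mask was offered. Those who can grow facial hair pick their style before and after the hospital's first COVID-19 cases. An attribution item follows, on whether the guidance influenced the respondent's facial hair. Two further items cover satisfaction and motive: "if they are happy with their current style, if they have any religious or culture reasons for maintaining their style". The item on personal effects closes this group and asks "whether there have been any religious, emotional or wellbeing effects to changing facial hair style". A favourite-style question comes next, "followed by any optional free text responses".

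The analysis in section 4 covers change in style only: "The odds ratio and relative risk will be calculated of a self-reported change in facial hair style". No analysis of the effects item is described. The questionnaire is listed in Appendix 1 but is not reproduced in the document.

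**The concern.** The group that section 3.1 singles out consists of doctors whose beliefs stop them removing facial hair. Many of them can be expected to have kept their style. The effects item, as described, asks about the consequences of changing style. Someone who changed nothing has no natural answer to it, however the guidance affected them.

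What is at stake is how the results are read. If few or no effects are recorded among doctors who kept their facial hair, that could reflect the wording of the item and still be taken as reassurance about the group of particular interest. Analysis cannot repair this. The survey is given once and is anonymous to the researchers, so nobody can be asked again.

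**Working it through.** The point concerns item content, so the check sets the aims beside the items described in section 4.

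**The protocol's own figure.** Section 5.2.1 expects 1025 × 0.20 = 205 responses. This reproduces exactly, but the point does not depend on it. The protocol gives no count or proportion of doctors who keep facial hair for religious or cultural reasons, so the gap cannot be expressed as a number of respondents.

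**What each item can record:**

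| Item in section 4 | Changed style, influenced by guidance (outcome in 3.2) | Kept style for religious or cultural reasons (group in 3.1) |
|---|---|---|
| Fit test, usual PPE, alternative offered | Practical consequence | Practical consequence |
| Style before and after | Shows a change | Shows no change |
| Influenced by FFP3 guidance | Attributes the change | Asks about the hair, not the effect on the person |
| Happy with current style | Satisfaction | Satisfaction |
| Religious or cultural reasons for keeping style | Reason | Reason; identifies the group |
| Religious, emotional or wellbeing effects | Applies | Does not apply as described: asks about changing |
| Free text | Optional | Optional |

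**Reading the table.**
1. The effects row is the only one that asks directly about religious, emotional or wellbeing effects. It serves the first column and not the second.
2. The satisfaction item is no substitute. A doctor may be content with a beard kept on religious grounds and still be distressed by what the guidance asks. Satisfaction with the style and the effect of the guidance can point in opposite directions.
3. Optional free text may bring out individual accounts. It gives no dependable proportion, because a blank does not mean that there was no effect.
4. Both subgroups can be identified from items already collected: style before and after, influence of the guidance, and reasons for keeping the style. Only the effect in the second subgroup is missing.
5. The effects item, as described, does not mention the guidance, whereas the outcome in 3.2 is limited to removal caused by it. The influence item would let the analyst apply that limit. The protocol does not say whether this will be done.

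**The case against.** The strongest reply is that section 4 only paraphrases the questionnaire. Exact stems, response options and routing cannot be checked, and section 5.3 says that questions are shown according to earlier answers. The real item may already cover people who changed nothing. This stands as a limit: the point concerns the item as the protocol describes it.

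A second reply is that the personal-impact outcome in 3.2 is defined for people who had to remove facial hair, so an item about change is right for it. That is correct, and the point does not rest on 3.2. It rests on 3.1, which names the effects on those who cannot remove facial hair. It can be argued that 3.1 is mainly about suitability, which the fit-test and alternative-PPE items address. Those items do give a countable answer on suitability. They do not give one on religious, emotional or wellbeing effects, which the survey sets out to ask about for those who changed.

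Two stronger readings are tempting and are not supported.
- A reader might infer that these doctors cannot report any effect. They can report a failed fit test, the absence of an alternative, dissatisfaction, their reasons, and anything in free text. Beliefs that forbid removal also need not forbid altering a style, and a doctor who did alter it can answer the effects item.
- A reader might infer that effects of changes unrelated to the guidance will be counted as impact of the guidance. No analysis of the effects item is stated, and the influence item allows such changes to be separated.

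**Conclusion.** The point holds in a limited form. As section 4 describes the survey, doctors who kept their facial hair for religious or cultural reasons have no structured item on which to report a religious, emotional or wellbeing effect of the FFP3 guidance, although section 3.1 singles them out. The gap is one item for one subgroup. Its numerical size is unknown, and assumed counts would add nothing.

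The conclusion assumes that section 4 reflects the content of the questionnaire, and that at least some doctors in the 3.1 group kept their style. If the appendix questionnaire already asks the question without requiring a change, only the description in section 4 needs correcting. It does not touch the planned odds ratios and relative risk for change in style. It is worth correcting because it is cheap before launch and cannot be put right afterwards.

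**What to change.** Before launch:

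1. Word the item around the guidance, for example: *Has the FFP3 facial hair guidance had any religious, emotional or wellbeing effect on you, whether or not you changed your style?*
2. Route it to every respondent who can grow facial hair, and check that the automatic display rules in section 5.3 do not hide it from those who reported no change.
3. Bring the description in section 4 into line with the questionnaire listed in Appendix 1.
4. Report the item separately for (a) those who changed style and said the guidance influenced them, which serves the outcome in 3.2, and (b) those who kept their style for religious or cultural reasons, which serves the objective in 3.1. The items that define both groups are already in the survey.

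The cost is one reworded question, with no added length to a survey of about five minutes, and one cross-tabulation. The small downside is that effects of style changes made for other reasons would no longer be recorded; measuring those is not a stated aim.
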